The dependent variable in each model (antihypertensive medications, glucose-lowering medications, statins) is a binary indicator of high medication adherence (e-PDC \geq 80%) and is predicted by a binary indicator of adherence intervention assignment. We will screen and include patient characteristics in the model when they are unbalanced by treatment arm. In supplemental analyses, we will extend the GLM approach described above by including random intercepts to evaluate potential clustering effects at the level of clinic and/or provider.

H1 will be supported if the intervention group effect β_1 is significant and positive, supporting the prediction that clinical encounters with the adherence intervention are more effective than encounters without them for increasing medication adherence. Treatment group heterogeneity by patient sex, age group, race, insurance class, and comorbidity count will be assessed by including interaction terms consisting of products of patient variables and the intervention indicator.

Hypotheses H1.1b and H1.2b posit that patients assigned to the adherence intervention will be more likely than control patients to have reduced SBP (H1.1b) and reduced A1C (H1.2b) in the 12 months following the index visit.

 $E(Y)_t = \beta_{00} + \beta_{10}(Intervention) + \beta_{01}(Time) + \beta_{11}(Intervention * Time) + \beta_{c0}(Covariates)$ The analytic model will be a generalized linear model with an identity link and normal error distribution. The dependent variable Y (SBP for H1.1b and A1C for H1.2b) is predicted by a binary indicator of intervention assignment, time (pre-intervention vs. post), and the interaction of intervention assignment and time. We will screen and include patient characteristics in the model when

they are unbalanced by treatment arm, and will evaluate the potential for clustering by clinic and/or provider. A significant intervention group-by-time interaction term (P < 0.05) and a pre-specified contrast

A significant intervention group-by-time interaction term (*P*<0.05) and a pre-specified contrast indicating more reduction in SBP (H1.1b) or A1C (H1.2b) in the intervention than the control arm will support the prediction that encounters with the adherence intervention are more effective than encounters without it for improving BP and glycemic clinical outcomes.

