Missing Data: All key analytic variables will be derived from EMR or health plan databases in which it is extremely rare for care-delivery information to be incompletely recorded. The primary endpoints for differential change in A1C and SBP by study arm will be analyzed using all available data at multiple time periods using direct likelihood-based ignorable methods obtained via generalized linear models, with no need to model the missing data process, and will yield valid inference when the outcome is missing at random.^{114,115} For H1.1a, H1.2a, H1.3, if preliminary analyses determine that patient covariates are predictive of missing outcome data, we will consider using one or more of the following strategies. We will include these variables as covariates so that the model is conditioned on these characteristics. We will assume that missing values represent failed trials (e.g., a failure to realize one of the binary outcomes), resulting in conservative estimates of intervention effects. Finally, multiple imputation procedures may be employed to accurately estimate parameters across multiple imputed data sets.

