9.4.9 EXPLORATORY ANALYSES

In tertiary/exploratory analysis, we evaluate the impact of the intervention on 10-year CV risk, other objective measures of medication adherence such as PDC, survey assessed patient self-reported adherence, and patient and provider experience and satisfaction as assessed by surveys and interviews. We will also explore differences in intervention use across patient subgroups based on age, gender, race and ethnicity and visit characteristics (such as type of visit, reason for visit, or provider). Treatment arm differences will be assessed using a general or generalized linear mixed-model approach as with the primary analysis, with link functions and error distributions determined by the distribution of each outcome.

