Patient and provider experience, satisfaction, facilitators and barriers to implementation will be evaluated using patient and provider surveys and qualitative interviews. Throughout the development and intervention periods, qualitative interviews with key stakeholders which may include clinic and pharmacy leaders, PCPs, clinic staff, pharmacists and patients will be conducted to assess end user experience, enhance design and maximize buy-in. Qualitative interviews may be recorded, transcribed and analyzed ethnographically until thematic saturation is achieved.¹³⁴ Post-implementation, a pharmacist and PCP survey will assess measures of satisfaction, knowledge, use of adherence information, and shared decision-making behaviors.^{135,136} Patient surveys will be conducted with a random sample of about 700 intervention and about 700 control patients. The surveys will be conducted in 2 phases, the first phase occurring within 2 to 4 weeks after index visit and the second phase 2 to 4 weeks after addition to the pharmacist registry to give ample time for the pharmacist outreach to be completed in the intervention subjects >=6 months after the index visit. The second survey sample will include only patients who responded to a question on the first survey consenting to be called again in 6 months for another survey. Surveys will be conducted in a sequential multimode design to simultaneously minimize costs and nonresponse error.^{137,138} Surveys will include questions pertaining to self-reported adherence, barriers to adherence,¹¹¹ shared decision making,¹¹² satisfaction¹¹³, and quality of provider communication.¹³⁹ The patient survey sample size assumes 50% response rates, consistent with those regularly achieved by HP Center for Evaluation and Survey Research, and is large enough to show significance based on results observed with these instruments in previous trials conducted by our research team and others. Existing scales with known psychometric properties will be used for surveys where available. Where no existing scales are available, questions will be developed using best practices to minimize measurement error.¹³⁹

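### The survey comparisons plan for 50% nonresponse but name no analysis that accounts for it, although index EMR and e-PDC data are stored for the patients sampled

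*Combined protocol and SAP*

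**What the plan says.** Section 9.4.9 sets the sample: "Patient surveys will be conducted with a random sample of about 700 intervention and about 700 control patients". Section 3 gives the total as up to 1,400 eligible patients. The response assumption is explicit: "The patient survey sample size assumes 50% response rates". The first survey comes 2 to 4 weeks after the index visit. The second is timed to allow pharmacist outreach to be completed, at 6 months or later, and its frame is narrower: "The second survey sample will include only patients who responded to a question on the first survey consenting to be called again".

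The stated measure against nonresponse concerns collection: "Surveys will be conducted in a sequential multimode design to simultaneously minimize costs and nonresponse error". For analysis, 9.4.9 says: "Treatment arm differences will be assessed using a general or generalized linear mixed-model approach as with the primary analysis". In that primary analysis (9.4.2) the covariate rule is: "We will screen and include patient characteristics in the model when they are unbalanced by treatment arm".

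The missing-data paragraph of 9.4.2 opens from the premise that "All key analytic variables will be derived from EMR or health plan databases". It then covers change in A1C and SBP by likelihood methods, and the binary e-PDC hypotheses (H1.1a, H1.2a, H1.3) by covariates, failure imputation or multiple imputation. Survey outcomes are not mentioned.

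The rank of self-reported adherence varies. The synopsis, Section 3 and 9.4.9 place it as tertiary or exploratory; 9.4.2 lists it among key secondary variables.

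**The concern.** Answering a survey happens after randomization. Once the comparison is limited to those who answered, randomization no longer guarantees that the arms are alike.

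Response could plausibly depend on arm. Before the first survey, intervention patients are targeted for printed tools that carry adherence alerts, whereas the control CDS contains no adherence information (6.1.1). Before the second, pharmacist outreach has been offered in one arm only. If these contacts change who is willing to answer questions about adherence, the arms can differ among responders without any effect on adherence, barriers or shared decision making.

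The protocol accepts the general principle: Section 10.1.1.1 supports the consent waiver partly by the selection that requiring consent would introduce. Survey participation is itself a selection step.

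At stake is the interpretation of the patient-reported comparisons. Greater patient involvement in medication decisions is the third objective in the synopsis, and the patient survey carries the planned patient-reported scale for it.

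**Working it through.** **1. Numbers contributing.** Inputs: 700 per arm and 50% response (9.4.9).
- Survey 1: 700 × 0.50 = 350 per arm.
- Survey 2: neither the agreement rate nor a separate response rate is given. Assuming 50% to 100% for each, 700 × 0.50 × 0.50 × 0.50 ≈ 88 up to 700 × 0.50 × 1 × 1 = 350 per arm. That is 12.5% to 50% of those sampled.

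**2. The plan's own figure.** The sample is justified by the statement that it "is large enough to show significance based on results observed with these instruments in previous trials". No effect size, SD, alpha or power is given for any survey outcome, so 700 per arm cannot be reproduced. For orientation only, assume control 50%, two-sided alpha 0.05 and 80% power, and solve d = 1.96√(2p̄(1−p̄)/n) + 0.84√((p₁q₁ + p₂q₂)/n):
- n = 350 per arm: d = 0.074 + 0.031 = 10.5 points.
- n = 700 per arm: d = 7.5 points.

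**3. Bias in a responder comparison (all response patterns assumed).** Let true adherence be p = 0.5 in both arms, with no intervention effect. Let rA and rN be the response rates of adherent and nonadherent patients. Adherence seen among responders is p·rA / (p·rA + (1−p)·rN).

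| Intervention rA/rN | Control rA/rN | Seen, intervention | Seen, control | False difference |
|---|---|---|---|---|
| 60/40 | 60/40 | 60% | 60% | 0 |
| 55/45 | 50/50 | 55% | 50% | 5 points |
| 60/40 | 50/50 | 60% | 50% | 10 points |

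With 350 per arm, SE ≈ √(0.5/350) = 0.0378. The chance of p < 0.05 is then about 26% for a false 5 points and about 75% for a false 10 points. In the first row the level is wrong but the difference is not, so the chance stays at 5%.

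**4. What data could adjust for this.** An e-PDC below 80% with moderate or high confidence is part of every eligibility route (5.1). Index and later encounter data, including adherence calculations, are stored for eligible patients (10.1.9.1). The algorithms run outside encounters at 6, 12 and 18 months in both arms (1.3). Index predictors therefore exist for nonresponders, at least for the qualifying medication. Follow-up e-PDC may be missing for some; the missing-data text of 9.4.2 allows for that.

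**5. Precision cost of weighting.** Take two equal strata of a recorded predictor with response rates a and b, and weights 1/a and 1/b. Effective n = (Σw)²/Σw² = 700² / (350/a + 350/b).
- 55%/45%: 346
- 60%/40%: 336
- 65%/35%: 318
- 70%/30%: 294

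The detectable difference from step 2 moves from 10.5 points to between 10.6 and 11.5.

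**6. How much bias weighting removes.** Suppose a binary EMR predictor agrees with true adherence 70% of the time (assumed). For intervention response of 55%/45%:
- Predictor positive: adherent share of responders = 0.7×0.55 / (0.7×0.55 + 0.3×0.45) = 0.385/0.520 = 0.740.
- Predictor negative: 0.3×0.55 / (0.3×0.55 + 0.7×0.45) = 0.165/0.480 = 0.344.
- Weighted back to equal strata: (0.740 + 0.344)/2 = 0.542.

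The false difference falls from 5 to 4.2 points. The same steps for 60%/40% take 10 points to 8.5. At 80% agreement, 5 points falls to 3.2.

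**The case against.** The strongest objection is that the proposed correction addresses little of the bias that the illustration displays. Section 2.2 says self-report may correlate poorly with refill-based measures, and e-PDC is such a measure. All sampled patients also entered with a qualifying e-PDC below 80%, which narrows the range of the main predictor. Step 6 bears this out, and the objection stands as a limit on the benefit.

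Second, nothing in the documents shows that adherence-related response differs by arm. This stands too: the size of the bias is assumed, and could be zero. Exposure before survey 1 is also only attempted, with a print-rate goal above 75% (5.5), and control patients receive the basic CDS.

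Third, modelling as in the primary analysis could be read generously, as importing the missing-data strategies of 9.4.2. An imbalance screen run among responders could also pick up a recorded characteristic that drives differential response. But those strategies are conditional, are written for H1.1a, H1.2a and H1.3, and start from a premise about EMR or health-plan data. The plan does not say in which set imbalance is screened. A mixed model can use a patient with one of two surveys; it gets nothing from a patient with neither.

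Fourth, a reader might infer that the plan prescribes a responders-only analysis, or that the patient survey is its sole evidence on patient involvement. Neither is supported. The first is inferred from silence: no stated method brings nonresponders in. On the second, 9.4.9 also plans a pharmacist and PCP survey covering shared decision-making behaviors, and interviews that may include patients.

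**Conclusion.** The gap is real and modest. The plan expects half of the survey sample not to answer, restricts the second survey further, and names no analytic handling of nonresponse, although index data on nonresponders are stored. Whether bias results depends on whether response relates to adherence differently by arm, which the documents do not tell us and the plan does not undertake to check.

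The 5- and 10-point false differences show what could happen under assumed response patterns. A reader might take the 26% and 75% rejection rates as the expected error of these comparisons, or as what weighting would remove. Neither follows: they disappear when the pattern is equal in both arms, and most of the bias would remain if recorded data predict adherence only moderately.

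The consequence is confined to survey outcomes, mostly ranked tertiary or exploratory. The primary endpoints come from EMR data and are unaffected. This is an inexpensive improvement and does not threaten the trial's main conclusions.

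**What to change.** Add to Section 9.4.9, for each survey:

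- Report response rates by arm, and the characteristics of responders and nonresponders by arm, from index EMR data and e-PDC.
- Estimate the arm difference with adjustment for nonresponse. Fit the probability of response separately by arm in all sampled patients on index variables (e-PDC, age, sex, race, insurance class, comorbidity count, visit count, condition cohort), weight responders by its inverse, and use robust standard errors. Multiple imputation with the same predictors is an acceptable alternative.
- For survey 2, add survey 1 answers and, where available, 6-month e-PDC. These are post-randomization, so they belong in the response or imputation model only, not as covariates in the outcome model.
- Present the adjusted and unadjusted results side by side, and interpret a survey difference as an intervention effect only if they agree. State that agreement does not rule out nonresponse driven by unrecorded factors.

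The cost is some SAP wording, modest analysis work on data largely already held, and the small loss of precision in step 5. The limit is that only nonresponse explained by recorded data is corrected, and the text should say so.

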10 SUPPORTING DOCUMENTATION AND OPERATIONAL CONSIDERATIONS

10.1 REGULATORY, ETHICAL, AND STUDY OVERSIGHT CONSIDERATIONS

10.1.1 INFORMED CONSENT PROCESS

10.1.1.1 CONSENT/ASSENT AND OTHER INFORMATIONAL DOCUMENTS PROVIDED TO PARTICIPANTS

As with previous CDS studies we have conducted, a waiver of consent for the study population will be requested for the following reasons¹⁰⁸:

a) All open treatment medication options identified by the intervention are U.S. Food and Drug Administration-approved and evidence-based, as specified in the regional and national clinical practice guidelines. No care is advocated that is not evidence-based.

Thus, the care conforms to current standards of care and ought not to represent any additional risk to patients beyond the routine risk that all patients assume whenever they have contact with the medical care system. The CDS system has been used to support diabetes, hypertension and lipid management in two previously completed randomized clinical trials with DSMB monitoring that revealed no safety concerns.

(b) The CDS identifies and gives safety warnings about drug-drug and drug condition that are potentially unsafe to the patient, which is of minimal risk to possible benefit to each patient at each visit during the study period.

(c) At clinic training sessions/communications and on printed decision support tools, we emphasize that it is inappropriate for a PCP to follow suggested treatment options without further checking the clinical status of a given patient. A disclaimer on the CDS says that treatment options are based only on electronically available data and are not intended to be a substitute for clinical judgment.

(d) It would be impractical to consent patients (due to large numbers of patients) and impossible to answer the primary research questions (due to selection effects related to consent) if written informed consent of all patients were required.

(e) Procedures are in place to opt out of pharmacist phone calls based on patient or provider preference.

(f) The intervention is supported by the care system's leadership, implemented with their collaboration and support, and embedded in the care process at the clinic and department level. Therefore, it would be accessible to all providers and pharmacists, with use of the tool indicating implied consent.

For the random sample of patients surveyed as part of the study, study information will be included in the survey invitation letter and survey introduction during the phone call, and implied consent will be assumed for survey responders. Informed consent will be obtained prior to any interviews.

In addition to the internal HealthPartners Institute policies, HIPAA itself makes specific provision for waiver of authorization to use protected health information (PHI) for research recruitment purposes under some specific conditions, all of which this study meets¹⁴⁰.

At HealthPartners, patients can opt out of use of their data for research. HealthPartners Institute keeps a record of the small number of individuals who have opted out to avoid use of their data or attempts to recruit them into studies. We will exclude patients from analysis who have declined permission for their medical records to be used in research.

10.1.1.2 CONSENT PROCEDURES AND DOCUMENTATION Not-applicable.

10.1.2 STUDY DISCONTINUATION AND CLOSURE

This study may be temporarily suspended or prematurely terminated if there is sufficient reasonable cause. Written notification, documenting the reason for study suspension or termination, will be provided by the suspending or terminating party to participating clinics, investigators, study team members and the funding agency. If the study is prematurely terminated or suspended, the Principal Investigator (PI) will promptly inform participating clinics, the Institutional Review Board (IRB), and sponsor and will provide the reason(s) for the termination or suspension.

Circumstances that may warrant termination or suspension include, but are not limited to:

- Determination of unexpected, significant, or unacceptable risk to participants
- Demonstration of efficacy that would warrant stopping
- Insufficient compliance to protocol requirements
- Data that are not sufficiently complete and/or evaluable
- Determination that the primary endpoint has been met
- Determination of futility

Study may resume once concerns about safety, protocol compliance, and data quality are addressed, and satisfy the sponsor and IRB.

10.1.3 CONFIDENTIALITY AND PRIVACY

In order to ensure patient confidentiality, we need to print the name of the patient on the CDS tools that are printed and given to the patient and their PCP at the time of a clinic visit. Because more than one nurse-PCP team may use the same printer, names are required to avoid mixing up printed materials and giving PHI to the wrong patient. It is also desirable to have each patient's name on this sheet of paper to ensure the patient knows that the information on the paper is personalized and related to his or her own health state. The technical aspects of this system are also relevant. The CDS system includes a Web service that applies a complex set of evidence-based algorithms and requires the patient name to create the materials that are subsequently displayed and printed within the EMR. Several measures are in place to ensure security of PHI: (1) Data transfer to and from the EMR, the Web service (at HealthPartners Institute), and the Web display (accessed at HealthPartners clinics and pharmacies and Goodrich pharmacies) uses a Simple Object Access Protocol (SOAP) with Secure Sockets Layer (SSL) encryption over Hypertext Transfer Protocol Secure (HTTPS); (2) The servers reside on an internal network protected by multiple firewalls; and (3) The Web server sits in the demilitarized zone (DMZ) so it can communicate with external systems. The rest of the processing and data storage occur on servers located inside the second firewall. No external system can access these servers directly, providing maximum security to the data that reside on these servers.

Although used for CDS display, patient names are scrubbed from the data nightly. The remaining data is retained in the operational data store for 2 weeks for immediate trouble shooting. Later, if needed for approved research, the data is moved to an analytic database with minimal access. With respect to the analytic databases, the following measures will be taken to protect PCPs and patients from the risk of breach of confidentiality: The patient name is not retained within the analytic database. A unique study ID code unrelated to the medical record number or other study subject-specific information will be assigned to each patient at the index visit (first visit in the intervention period). The study ID is used to link data from patient encounters over time and various data sources that are needed for analysis. A crosswalk table linking this code number to a PCP or patient name or medical record number will be destroyed within 12 months after completion of the linked databases needed to test study hypotheses.

In compliance with HIPAA regulations¹⁴⁰, no personally identifiable health information (PHI) will be shared outside of the affiliated covered entities (ACE) without obtaining a data use agreement or business associates agreement. HealthPartners Institute and HealthPartners are each one component of a larger organization defined as an ACE under HIPAA regulations. This allows researchers at the Institute to use HealthPartners medical records data for purposes such as those in this study in compliance with HIPAA regulations (i.e., following the concept of "minimally necessary" use of PHI).

The study team has extensive experience in health services research and clinical research with human subjects, with procedures to safeguard privacy and personal information. All study records are protected by:

- Locked storing all paper records in a secure location
- Use of untraceable study ID numbers instead of names wherever possible
- Password protection as well as firewalls
- Strong user login authentication on all electronic devices
- Physical security for all electronic devices containing personal information

Data will be retained in secure storage following the completion of the study in accordance with Minnesota and federal law. We guard against the potential for breach of subject confidentiality through a multi-layered system of data protection policies, processes, staff training, software safeguards and physical security measures for both paper and electronic data involved in research.

The following measures will be taken to protect subjects from the risk of breach of confidentiality:

• All data collected in the study will be identified by using a previously assigned arbitrary and unique subject identification number to each participant.

• A file containing a link between the study ID and individually identifying information will be maintained at by a programmer who is member of the study team through the conclusion of the study.

• A cross-walk table linking the study ID to a patient identity will be destroyed within 12 months after the linked databases needed to test study hypotheses are completed.

• All electronic study data will be maintained in a computerized database residing on a username- and password-protected file-server to which only the researchers involved in the study will have access.

• All study-related paper documents containing individually identifiable information will be maintained in locked file cabinets.

To protect the confidentiality of any HealthPartners employees participating in an interview, we will not allow anyone outside of the research team to know the identity of those interviewed. All of the protection to electronic data sources, described above, also apply to the interview audio recordings and transcripts.

Certificate of Confidentiality:

To further protect the privacy of study participants, a Certificate of Confidentiality will be issued by the National Institutes of Health (NIH). This certificate protects identifiable research information from forced disclosure. It allows the investigator and others who have access to research records to refuse to disclose identifying information on research participation in any civil, criminal, administrative, legislative, or other proceeding, whether at the federal, state, or local level. By protecting research participants,

Certificates of Confidentiality help achieve the research objectives and promote participation in studies by helping assure confidentiality and privacy to participants.

